4.5. Informed Consent

The process of assuring that individuals are making an informed decision about participating in this study includes both verbal and written communication. The consent form will be reviewed with participants and the participant will be given time to review the written consent form and ask questions. The participant will be given a copy of their signed consent forms.

Participants will also be informed about the common adverse effects of study drugs and it will be recommended that they stop eating once they feel satiety to decrease the risk of nausea and vomiting during the treatment period. Study subjects will receive standard medical care from their endocrinologist, but the study team will closely monitor the patients to assess adverse events. At these phone or email contacts and at the study visits, the frequency of hypoglycemia will be documented. Hypoglycemia will be assessed following consensus definition (Agiostratidou, 2017). Three levels of hypoglycemia will be recorded. Level 1: glucose < 70 mg/dl (3.9 mmol/l) and glucose \geq 54 mg/dl (3.0 mmol/l). Level 2: glucose < 54 mg/dl (3.0 mmol/l) and Level 3: a severe event characterized by altered mental and/or physical status requiring assistance.

4.6. Description of Treatment Groups

This open label protocol will enroll a total of 56 participants who will be randomly assigned (1:1) to the following groups:

- 28 participants will be assigned to receive Omega-3 Fatty Acids and Vitamin D combination following randomization, and then will be followed for an additional year.
- 28 participants will receive only Vitamin D.

4.7. Treatment Assignment

Eligible participants who have provided written informed consent will be randomized to one of the treatment groups. The participant, the clinical investigator and clinical personnel will be known to the treatment assignment.

4.8. Study Assessments

During the course of the study, participants will frequently undergo assessments of their insulin production, immunologic status, overall health and well-being and diabetes care (see schedule of assessments in Appendix 1). The participant's insulin production will be assessed by C-peptide measurements during mixed meal glucose tolerance tests (MMTT) conducted as per the study schedule. The MMTT will consist of a standard liquid meal (Boost Plus®, Nestlé HealthScience) at a dose of 6 mL/Kg to a maximum of 360 mL. The participant's diabetes control will be evaluated by measuring glycosylated hemoglobin (HbA1c) every four months.

Remaining samples will be stored in the Diabetes Research Institute for future analysis. Samples will be stored only with the participant's permission. Participants who decline consent for storage of remaining samples will still be eligible to participate in this study.

4.9. Post-treatment Follow-up

All subjects will be treated with supplement combination or vitamin D alone over a one year period. Subjects will also be asked to undergo additional follow-up post-treatment for up to one year with a visit every 4 months.

5. PATIENT MANAGEMENT

5.1. Recruitment and Screening

Information about the clinical trial will be made available to potential participants as follows: a) flyers at the Diabetes Research Institute and the Mailman Center for Child Development, University of Miami, b) on-line at www.Clinicaltrials.gov and Diabetes Research Institute Foundation website www.diabetesresearch.org, c) social media: Diabetes Research Institute Foundation Facebook and twitter accounts and YouTube channel, d) by press release(s) from the Diabetes Research Institute, University of Miami.

We will also provide information about the clinical trial to physicians within the Adult and Pediatric Divisions of Endocrinology, Diabetes and Metabolism at the University of Miami. We expect this approach to result in widespread awareness of this clinical trial and lead to successful recruitment numbers.

After informed consent is obtained, subjects will undergo assessments to determine if they meet eligibility criteria. Documentation of the subjects understanding of the risks and benefits of the study will also be discussed during the informed consent process.

5.2. Randomization

Individuals complying with all inclusion and exclusion criteria and consenting to study participation will be randomized at the clinical site. A blinded statistician will create color and number coded envelopes using a stratified blocked randomization (new diagnosis vs established, child vs adult). Each envelope will contain a card with the corresponding treatment group assignment. Envelopes will be kept in a file cabinet in a secured room at the Diabetes Research Institute. The study PI will perform the randomization of all newly enrolled subjects in a 1:1 ratio to each of the two arms by selecting the corresponding color and number coded envelope to ensure these factors are equally distributed across the two arms of the intervention.

For each subject, the Subject Identificaton Number (SIN), treatment and participant's name will be entered into the study log.

5.3. Intensive Diabetes Management

During the study period, all participants will receive "intensive" management of their diabetes. The goal of the treatment will be to keep the HbA1c levels within the currently recommended American Diabetes Association target range in the absence of level 3 hypoglycemia or diabetic ketoacidosis. The primary responsibility for diabetes management will be the treating or referring diabetes care provider, but the research study team will provide close additional support through regular interaction at study visits. Subjects will not be permitted to use non-insulin pharmaceuticals for glycemic control.

Glucose levels should be checked frequently using either a continuous glucose monitor (CGM) or manually via study participant's glucometer. In addition, subject will complete a 7-day Blood Sugar record and Hypoglycemia log at the screening visit (+/- 7 days) and at each study visit (+/- 7 days) starting at visit 2. Subjects using a CGM can use glucose values from the CGM to complete the 7-day blood sugar record. If subjects are using an insulin pump, pump data will be downloaded to document insulin use. Subjects on multiple daily injections will record their insulin use on the 7-day blood glucose record unless they are using a smart insulin pen with capability to record insulin dosing in which case data will be downloaded from the device and serve as the insulin dosing documentation. If patient is using a CGM and pump, downloaded data from pump and CGM will be used instead of the 7-day blood sugar log. Data obtained from participants' diabetes management devices and blood sugar log will serve as source documentation of glucose monitoring and insulin use. The study team will be evaluating the HbA1c data and provide additional guidance to the participants as needed to bring diabetes control within goals. Any episodes of level 3 hypoglycemia will prompt review by the study physician and site medical monitor with recommendations, if any, for changes in diabetes management conveyed to the participants in conjunction with the principal investigator(s).

5.4. Administration of Study Drugs

Due to current status of COVID-19 pandemic, clinical research activites have been affected and are being conducted as recommended by institutional guidelines to minimize potential exposure to SARS-CoV-2 for both research subjects and clinical research study team. Study investigational product(s)

may be mailed to participants as determined by PI. For international patients, they may be able to obtain over the counter vitamin D3 and/or omega 3 fish oil locally (in their country of residence) if the investigational product cannot be mailed overseas (at the discretion of the PI).

In addition, the study team will try to conduct as much as possible “remote” study visits (e.g telephone communication, video conferencing, obtaining study test results from Quest Diagnostics Lab) to obtain required SOE information.

To appropriately gauge the dose of omega 3 fatty acids we are proposing the use of the AA/EPA ratio to guide dosing. As noted above, AA/EPA ratios in the 1.5 to 3.0 range have been studied in healthy volunteers and in children with ADHD have shown an association with clinical outcomes and noted to be safe. Further, such low ratios can be achieved by diet alone as documented in the Japanese population where the average fish consumption has been reported to be one serving of 85 g (3 oz; 900 mg EPA and DHA) per day and 90% of individuals eat fish at least once a week [7].

In view of the chronic nature of the immunopathogenesis of type 1 diabetes it is then not unexpected that therapeutic interventions started at disease onset to preserve beta cell function have usually been administered for a duration of 6 month to 2 years [8-10]. It is important, however, to highlight that one of the main factors responsible for determining the duration of therapy is the safety profile of the proposed intervention.

Data from TrialNet intervention trials has allowed to study the decline in C-peptide 2 years following type 1 diabetes onset which shows a biphasic profile with a steeper decline during the first year [11] suggesting that processes involved with beta-cell loss may be more aggressive during the first year of diagnosis. Thus, therapies aimed to preserve beta-cell function in new onset disease may likely need to be administered over a prolonged period of time and for at least 1 year following disease onset.

In established disease, duration of therapy is also dependent on the mechanism of the intervention and the safety profile. Since inflammation affecting glycemic control may be a chronic state in patients with type 1 diabetes and in view of the reportedly safety profile of high-dose omega 3 fatty acids, we have proposed treating patients with established type 1 diabetes for a duration of 1 year.

5.4.1.1. Ultra-refined omega-3 EPA/DHA concentrate (ZoneLabs® OmegaRx®2 Fish Oil) Administration

Participants will receive ultra-refined omega-3 EPA/DHA concentrate (ZoneLabs® OmegaRx®2 Fish Oil – Liquid; containing 3375 mg EPA+DHA [2250 mg EPA and 1125 mg DHA] in 5 mL).

Research subjects will be started at a dose of 150 mg of EPA+DHA per Kg body weight.

For example:

- The dose for a 22.5 Kg child will be:
 $150 \text{ mg} \times 22.5 \text{ Kg} = 3375 \text{ mg}$ of EPA+DHA fish oil corresponding to 5 mL of Omega Rx ®2 Fish Oil Liquid.
- The dose for a 30 Kg child will be:
 $150 \text{ mg} \times 30 \text{ Kg} = 4500 \text{ mg}$ of EPA+DHA fish oil corresponding to 6.7 mL of Omega Rx ®2 Fish Oil Liquid.

Participants who are unable to tolerate the liquid formulation will be switched to the OmegaRx®2 capsule formulation at the same dose as described above.

It is 150 mg of combined EPA and DHA per kg body weight to be given either as a single or divided into smaller doses through the day.

5.4.1.2. Modification or Discontinuation of omega-3 EPA/DHA concentrate

Dose will be adjusted to maintain a target AA/EPA ratio of 1.5-3.0 as follows:

- If AA/EPA ratio is ≥ 7 , double the dose and recheck ratio in one month
- If AA/EPA ratio is 4-6, increase dose by 50% and recheck ratio in one month
- If AA/EPA ratio is at target, maintain dose as prescribed
- If AA/EPA ratio is <1.5 , reduce dose by 50% and recheck in one month

AA/EPA ratios will be monitored monthly until achieving target levels and as per protocol or as clinically indicated thereafter.

5.4.1.3. Discontinuation of omega-3 EPA/DHA concentrate

Subjects would be continuously evaluated for any untoward effects of Omega-3 fatty acid supplements or negative side effects. Typically side effects consist of minor gastrointestinal symptoms, such as belching, indigestion, or diarrhea, stomach pain or discomfort, burping, heartburn, vomiting, constipation, nausea, and change in the sense of taste. Joint pain may be a side effect as well.

Patients with coagulation, bleeding, or blood disorders will be excluded. We will monitor clotting times of enrolled subjects by measuring the prothrombin time (PT/PT-INR) during all subject visits (except for visit 1), in addition to CBC with differentials (see schedule of assessment).

Symptomatic management of the side effects will be evaluated by the study physician and should the investigator believes that the study treatment is no longer in the best interest of the participant, subjects would be discontinued from the treatment. Similarly, if subject begins taking medications that affect clotting chronically, subjects would be discontinued and appropriately noted in the study record. Participants who prematurely discontinue study treatment will remain in the study and undergo all efficacy and safety assessments.

5.4.2. Vitamin D

Vitamin D is a nutrient found in some foods that is needed for health and to maintain strong bones. It does so by helping the body absorb calcium (one of bone's main building blocks) from food and supplements. People who get too little vitamin D may develop soft, thin, and brittle bones, a condition known as rickets in children and osteomalacia in adults.

Vitamin D is important to the body in many other ways as well. Muscles need it to move, for example, nerves need it to carry messages between the brain and every body part, and the immune system needs vitamin D to fight off invading bacteria and viruses. Together with calcium, vitamin D also helps protect older adults from osteoporosis. Vitamin D is found in cells throughout the body.

5.4.2.1. Vitamin D Administration

Vitamin D supplementation

1. For levels of Vitamin D 25OH of 30 -39 ng/ml:
 - a. age ≤10 years give 500 IU daily
 - b. age >10 years give 1000 IU daily
2. For levels of Vitamin D 25OH of 20 – 29 ng/ml give 50,000 IU weekly for 2 months and then:
 - a. age ≤10 years give 1000 IU daily
 - b. age >10 years give 2000 IU daily
3. For levels of Vitamin D 25OH of < 20 ng/ml give 50,000 IU weekly for 4 months and then:
 - a. age ≤10 years give 1000 IU daily

- b. age >10 years 2000 IU daily

Repeat vitamin D 25OH levels 1 week after the last 50,000 IU dose:

- For children whose levels are not above 30 ng/ml on repeat testing, repeat treatment as above.
- For children whose levels are 30 -39 ng/ml on repeat testing:
 - if age ≤10 years increase vitamin D supplementation to 1000 IU daily
 - if age is >10 years give 2000 IU daily

Thereafter, monitor vitamin D 25OH levels every 4 months (or more frequently at the discretion of the investigator) and adjust Vitamin D treatment to maintain levels > 40 ng/ml.

Study participants with or without a history of vitamin D deficiency who are on vitamin D replacement will continue their current dose if 25OH vitamin D levels checked at screening are in line with study targets. This may defer from the doses indicated above which apply to participants who are not on vitamin D replacement. Doses will then be adjusted at the discretion of the Principal Investigator in order to maintain 25OH vitamin D levels >40 ng/mL.

The Dietary Reference Intake Committee to Review Dietary Reference Intakes for Vitamin D and Calcium from Institutie of Medicine, recommends following upper intake levels for Vitamin D (see page 403-477)(https://www.ncbi.nlm.nih.gov/books/NBK56070/pdf/Bookshelf_NBK56070.pdf)

Table Representing Tolerable Upper Intake Levels (ULs) for Vitamin D				
Age	Male	Female	Pregnancy	Lactation
0–6 months	1,000 IU (25 mcg)	1,000 IU (25 mcg)		
7–12 months	1,500 IU (38 mcg)	1,500 IU (38 mcg)		
1–3 years	2,500 IU (63 mcg)	2,500 IU (63 mcg)		
4–8 years	3,000 IU (75 mcg)	3,000 IU (75 mcg)		
≥9 years	4,000 IU (100 mcg)	4,000 IU (100 mcg)	4,000 IU (100 mcg)	4,000 IU (100 mcg)

Microcrystalline cellulose is the only excipient in Biotech Pharmacal Vitamin D3 capsule with following quantities:

- D3-5000 IU capsule contains 89 mg of microcrystalline cellulose
- D3-1000 IU capsule contains 92.8 mg of microcrystalline cellulose
- D3 50,000 IU capsule contains 115 mg of microcrystalline cellulose

Type of microcrystalline cellulose is Vivapur Type 101, it is pure microcrystalline cellulose that meets the requirements for Ph. Eur, NF, and JP monographs for Microcrystalline Cellulose and it complies with E460 (i) monograph and FCC as well.

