II	Fourteen (14) adults (18-65 years) of new-onset T1D diagnosed within last 6 months (\leq 180 days)																				
III	Fourteen (14) children (6-17 years) of established T1D of more than 6 months duration (>180 days) and up to 10 years																				
IV	Fourteen (14) children (6-17 years) of new-onset T1D diagnosed within last 6 months (\leq 180 days)																				
Drugs with route of administration	Dose	Arm A	Arm B																		
Ultra-refined omega-3 EPA/DHA concentrate in Liquid or	Based on the body weight of the participant Initial Dose:	Three times daily orally																			

	
Capsule formulations (ZoneLabs® OmegaRx®2 Fish Oil – Liquid; containing 3375 mg EPA+DHA [2250 mg EPA and 1125 mg DHA] in 5 mL
 
Of note, each 1 mL of OmegaRx®2 contains 675 mg of EPA+DHA.
	
150 mg of EPA+DHA per Kg body weight.
 
Maintaince Dose: Dose will be adjusted to maintain a target AA/EPA ratio of 1.5-3.0. AA/EPA ratios will be monitored monthly until achieving target levels and as per protocol or as clinically indicated thereafter.
 
It is 150 mg of combined EPA and DHA per kg body weight to be given either as a single or divided into smaller doses through the day.
		
	
Vitamin-D 25OH (Cholecalciferol)
	
Based on the Vitamin D level and age of the participant
 
For levels 30 -39 ng/ml:
 
Age ≤10 years give 500 IU daily
 
Age >10 years give 1000 IU daily
 
For levels 20 – 29 ng/ml
 
50,000 IU weekly for 2 months and then:
 
Age ≤10 years give 1000 IU daily
 
Age >10 years give 2000 IU daily
 
For levels < 20 ng/ml
	
Daily orally
	
Daily orally

		
50,000 IU weekly for 6 months and then:
 
Age ≤10 years, give 1000 IU daily
 
Age >10 years, give 2000 IU daily
 
Dose will be adjusted and monitored every four months until achieving target levels and as clinically indicated thereafter.
		
Treatment Description	Subjects will be randomized to one of the two arms. The treatment arm A includes Omega-3 Fatty Acids and Vitamin D. The subjects randomized in Arm B (control group) will receive only Vitamin D supplement. The treatment assignment will be conducted in a open label fashion.			

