5.4.2.2. Modification or Discontinuation of Vitamin D

Vitamin D is likely safe when taken by mouth in recommended amounts. Most people do not commonly experience side effects with vitamin D, unless too much is taken. Some side effects of excess vitamin D include weakness, fatigue, sleepiness, headache, loss of appetite, dry mouth, metallic taste, nausea, and vomiting.

Taking vitamin D for long periods of time in doses higher than 4000 units daily is possibly unsafe and may cause excessively high levels of calcium in the blood. However, much higher doses are often needed for the short-term treatment of vitamin D deficiency.

Vitamin D in very high doses can make the intestines absorb too much calcium which can cause high levels of calcium in the blood (hypercalcemia). This can cause side effects including nausea, vomiting, constipation, poor appetite, weakness, weight loss, confusion and disorientation. Hypercalcemia can also lead to kidney stones, damage to the kidneys, and cause calcium deposits in heart and lungs. We will monitor blood levels of vitamin D to minimize the risk of these side-effects.

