5.4.2.3. Contraindications for Vitamin D Supplement

There are conditions where Vitamin D treatment require special precautions and these subjects will not be included in this study:

Kidney disease: Vitamin D may increase calcium levels and increase the risk of arteriosclerosis" in people with serious kidney disease. This must be balanced with the need to prevent renal osteodystrophy, a bone disease that occurs when the kidneys fail to maintain the proper levels of calcium and phosphorus in the blood.

Sarcoidosis: Vitamin D may increase calcium levels in people with sarcoidosis. This could lead to kidney stones and other problems..

Histoplasmosis: Vitamin D may increase calcium levels in people with histoplasmosis. This could lead to kidney stones and other problems..

Over-active parathyroid gland (hyperparathyroidism): Vitamin D may increase calcium levels in people with hyperparathyroidism..

Lymphoma: Vitamin D may increase calcium levels in people with lymphoma. This could lead to kidney stones and other problems..

Tuberculosis: Vitamin D might increase calcium levels in people with tuberculosis. This might result in complications such as kidney stones.

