5.4.6. Discontinuation of study drug(s) in an individual patient

The dosing and administration of investigational medication according to study specification will be discontinued for an individual participant if any of the following criteria is met:

- Subjects who have 3 severe hypoglycemic reactions on separate days (requiring assistance from another individual)
- Subjects who have nausea or vomiting that precludes adherence to diet will discontinue the use of the study drug.
- Subjects who lose more than 10 kg in weight from baseline.

- Any grade 3 or higher AE occurs that, based on the medical judgment of the investigator, the medical monitor, and the clinical trial physician, prevents completion of the course of study treatment.
- Any unexpected, treatment-related SAE resulting in permanent treatment discontinuation and not related to glycemic events.
- The investigator determines that it is in the participant's best interest to discontinue treatment.
- The participant, or participant's legal representative, requests that treatment be halted.
- The participant becomes pregnant.

Further care will be provided according to the judgment and practice of the investigator. The participant will be asked to remain in the study and participate in follow-up. If study treatment is discontinued, the medical monitor will be notified. Participants who prematurely terminate from the study will not be replaced.

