6.5. Laboratory Assessments

The following laboratory assessments will be performed during the study:

- Chemistrys (sodium, potassium, chloride, CO₂, glucose, BUN, creatinine)
- Liver function tests (ALT, AST, alkaline phosphatase, total protein, albumin, total and direct bilirubin)
- Hematology (complete blood count with differential, platelets, Prothrombin time [PT/PT-INR])
- Pregnancy test as appropriate
- Autoantibodies (IA2, GAD65, ZnT8, insulin autoantibodies are induced by insulin injections and thus are not useful at this stage)
- Samples for serology (i.e. Hepatitis B, Hepatitis C, EBV, CMV and Human Immunodeficiency Virus) and HbA1c
- 4-hours Mixed Meal Tolerance Test (MMTT)
- Samples for 25OH vitamin D levels and AA/EPA ratio

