6.16. Stopping rules

As stated earlier, the progress of the study will be monitored by the DSMB which will review safety data and make recommendations regarding continuation, termination, or modification of the study. Based on a 12 month enrollment period and an additional study period of 12 months, the DSMB will formally review the safety data after participant number 24 reaches day 90 of the study. The number of subjects who discontinue study treatment will also be included in the reports prepared for the DSMB.

In addition, safety data will be reviewed by the DSMB when an event occurs that is of sufficient concern to the medical monitor and/or study investigator(s) to warrant review, or when an event occurs that contributes to a stopping rule listed below.

- **Patient stopping rules:** Subjects who have 3 severe hypoglycemic reactions (requiring assistance from another individual) on separate days or who have nausea or vomiting that precludes adherence to diet will discontinue the use of the study drug. Subjects who lose more than 10 kg will also discontinue study drug. Subjects who discontinue the drug treatment will not be replaced.
- **Trial stopping rules:** Interim analysis will be conducted when recommended by the DSMB to review safety data, including metabolic, immunological assessments and adverse events. The DSMB may recommend early stopping if there is sufficient evidence to conclude that the investigational treatment is harmful based on interim analysis of safety endpoints.

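### Below 20 ng/mL, Table 1 and section 5.4.2.1 give different vitamin D loading courses (6 and 4 months), and no required test measures calcium

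*Combined protocol and SAP*

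**What the plan says.** Two places set the loading course for 25OH vitamin D below 20 ng/mL:

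- Section 5.4.2.1: "For levels of Vitamin D 25OH of < 20 ng/ml give 50,000 IU weekly for 4 months".
- Section 1.1, Table 1: "50,000 IU weekly for 6 months and then" the daily maintenance dose.

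Both then give 1000 IU daily at age 10 or under and 2000 IU daily above age 10. They also agree on the 20-29 ng/mL tier (2 months of loading) and the 30-39 ng/mL tier.

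On safety, section 5.4.2.2 describes hypercalcemia as the consequence of too much vitamin D, with kidney stones, kidney damage and calcium deposits to follow. Its stated protection is "We will monitor blood levels of vitamin D to minimize the risk of these side-effects". The chemistry in section 6.5 is itemised as "Chemistrys (sodium, potassium, chloride, CO₂, glucose, BUN, creatinine"). Calcium is not there, nor in the liver or hematology lists, nor a row in the schedule of events (Appendix A).

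**The concern.** Staff who dose from Table 1 and staff who dose from section 5.4.2.1 would give the same participant loading courses of different length. Vitamin D is the only study agent in Arm B and part of Arm A, and half of the planned participants are children.

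The harm that the protocol itself names is also not measured by any required test. Section 5.4.2.2 is headed as the place for modification or discontinuation, but it gives no calcium value and no upper 25OH vitamin D value at which dosing changes. Section 5.4.2.1 sets a target above 40 ng/mL with no ceiling. The other agent is handled differently: section 5.4.1.2 halves the omega-3 dose when the AA/EPA ratio falls below 1.5, and section 5.4.1.3 pairs the bleeding risk with a clotting test.

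**Working it through.** **Inputs.** Weekly dose 50,000 IU; 4 or 6 months (section 5.4.2.1; Table 1); maintenance 1000 or 2000 IU daily by age (both places); end of treatment at day 360 (Appendix A). The documents do not define a month in doses, so I use a range: 4 weeks per month gives 16 and 24 doses, and calendar months give 17 and 26.

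**Loading dose** = doses × 50,000 IU.

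- 4 months: 16 × 50,000 = 800,000; 17 × 50,000 = 850,000 IU.
- 6 months: 24 × 50,000 = 1,200,000; 26 × 50,000 = 1,300,000 IU.
- Difference: 8 to 9 doses, 400,000 to 450,000 IU. Ratios: 24/16 = 1.50 and 26/17 = 1.53.

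**Treatment-year total** = loading dose + (360 − 7 × doses) × daily maintenance, with no re-titration.

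| Course | Loading days | Maintenance days | Total, age >10 (IU) | Total, age ≤10 (IU) |
|---|---|---|---|---|
| 4 months, 16 doses | 112 | 248 | 800,000 + 496,000 = 1,296,000 | 800,000 + 248,000 = 1,048,000 |
| 4 months, 17 doses | 119 | 241 | 850,000 + 482,000 = 1,332,000 | 850,000 + 241,000 = 1,091,000 |
| 6 months, 24 doses | 168 | 192 | 1,200,000 + 384,000 = 1,584,000 | 1,200,000 + 192,000 = 1,392,000 |
| 6 months, 26 doses | 182 | 178 | 1,300,000 + 356,000 = 1,656,000 | 1,300,000 + 178,000 = 1,478,000 |

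Differences, matching the month convention (24 against 16 doses, 26 against 17):

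- Age >10: 288,000/1,296,000 = 22.2%; 324,000/1,332,000 = 24.3%.
- Age ≤10: 344,000/1,048,000 = 32.8%; 387,000/1,091,000 = 35.5%.

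A 365-day year leaves the IU differences unchanged and lowers each percentage by less than 0.2 points.

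**Calcium: safeguards set side by side.**

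| Existing safeguard | What it detects |
|---|---|
| 25OH vitamin D levels (5.4.2.1, 5.4.2.2) | Exposure, not calcium |
| BUN and creatinine (6.5) | Kidney effect, after the fact |
| Excluded conditions (5.4.2.3) | Known predisposition; no baseline calcium is listed |
| Nausea or vomiting stop (5.4.6, 6.16) | Symptoms |
| Weight-loss stop (5.4.6, 6.16) | Loss of more than 10 kg |
| Investigator discretion, grade 3 or higher adverse events (5.4.6) | Judgment; no calcium level |
| Laboratory abnormalities recorded as adverse events (7.1.10) | Only what was measured |

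None requires a calcium result.

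**The case against.** The strongest reply has three parts.

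First, the conflict is one number. The weekly dose, maintenance dose and target agree, section 5.4.2.1 is the detailed administration text, and dosing follows levels checked every 4 months, so a 6-month course would be reviewed before it ended. That limits the consequence but does not say which duration applies. A reader might infer that the participant receives 50% more vitamin D. That is true of the loading dose only; maintenance brings the year's difference down to the figures above. The gap can move further: section 5.4.2.1 repeats the treatment for children whose retest is not above 30 ng/mL, so another 2- or 4-month course could close or reverse it.

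Second, the sponsor chose to control exposure through 25OH vitamin D, and other protections exist. Section 5.4.2.3 lists conditions in which "Vitamin D treatment require special precautions and these subjects will not be included in this study". Section 5.4.6 adds "Subjects who have nausea or vomiting that precludes adherence to diet will discontinue the use of the study drug", and section 6.16 adds "Subjects who lose more than 10 kg will also discontinue study drug". A laboratory panel may report calcium anyway. These points stand, and for that reason the calcium test is an improvement rather than the correction of an error. They remain indirect, and no text requires the result or says what to do with it.

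Third, the loading dose itself might look unsafe: 50,000/7 is about 7,143 IU a day, above the 3,000 and 4,000 IU upper intake levels tabulated in section 5.4.2.1 for ages 4-8 and 9 or over. The documents do not support calling that an error, because section 5.4.2.2 accepts that "much higher doses are often needed for the short-term treatment of vitamin D deficiency".

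Two further inferences fail. One is that scheduled chemistry follows a 4-month course closely. With last doses on days 106-113 and the ±14-day window of section 6.8, the month-4 sample (days 106-134) falls anywhere from 7 days before to 28 days after the last dose. The month-8 sample (days 226-254) falls 50 to 92 days after a 6-month course (last dose on days 162-176). Visit timing therefore does not favor either duration. The other is that section 8.1 already requires a normal repeat value: it also accepts an abnormal result that can be explained when safety is not at risk.

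**Conclusion.** The duration conflict is an error in current text and should be corrected. Its size is about 50% of the loading dose, and 288,000-387,000 IU over the treatment year. That rests on full adherence, the stated range for doses per month, and no re-titration or repeat course. The documents do not give the share of participants below 20 ng/mL, so no head count is claimed. Participants already on replacement with levels in line with study targets keep their dose and are not affected.

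The missing calcium test and action level are a gap in safety monitoring that is cheap to close. Neither point implies bias: the same vitamin D rules apply in both arms.

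**What to change.** 1. State one loading duration for levels below 20 ng/mL in both Table 1 and section 5.4.2.1. The sponsor confirms which; the default is the 4 months of section 5.4.2.1. Cost: one number.
2. Add serum calcium to the chemistry in section 6.5, on the sample already drawn at screening and months 4, 8 and 12, and review the screening value before the first dose. Cost: one analyte on the 3.5 mL tube already collected (Appendix B). Albumin, which helps in reading calcium, is already measured.
3. Add a hold rule to section 5.4.2.2: vitamin D is held when calcium is above the laboratory's upper limit and a repeat test confirms it. It resumes once calcium is normal, or once the result is explained and poses no safety risk, in line with section 8.1. This level is my proposal, not the protocol's; the sponsor and DSMB may set another.
4. Optional: run calcium on the retest that section 5.4.2.1 requires 1 week after the last loading dose, for every loading tier.

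The downside is an occasional repeat draw or held dose. As an illustration, assume that the upper limit is a 97.5th percentile and that the month-4 and month-8 tests are independent. Then 1 − 0.975² = 4.9% of participants, or 0.049 × 56 ≈ 2.7 people, would have a first flag by chance; confirmation on repeat reduces the number actually held. The month-12 value comes at the end of treatment, so it informs follow-up rather than dosing.
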